# **15.0 BIOMARKER ANALYSES**

## **15.1 Peripheral Blood Biomarker Correlative Studies**

### **15.1.1 Serum Cytokines**

Serum cytokines will be measured in the Immune Monitoring Laboratory (IML), Fred Hutch. Cytokines to be measured include IFN- $\gamma$ , TNF- $\alpha$ , GM-CSF, and IL-6 by Luminex bead assay.

### **15.1.2 Collection of specimen(s)**

Whole blood will be collected into one 10 mL serum separator tube.

#### **15.1.2.1 Handling of specimen(s)**

Specimens will be collected at room temperature.

**15.1.2.2 Shipping of specimen(s)**

Specimens will be shipped at ambient room temperature to the IML, Fred Hutch.

**15.1.2.3 Site performing correlative study**

The serum cytokine assay will be performed by the IML, Fred Hutch.

**15.1.3 Peripheral blood for storage**

In addition to samples collected above, up to 40 mL of additional peripheral blood will be collected prior to cycle 1 day 1 of study drug, and weekly thereafter for 4 weeks, then every cycle for cycles 2-6. This will be stored for future analyses of biomarkers or other molecular correlates, to be determined.

**15.1.3.1 Collection of specimen(s)**

Whole blood will be collected into up to four 10 cc EDTA tubes.

**15.1.3.2 Handling of specimen(s)**

Samples will be collected at room temperature, followed by Ficoll separation and frozen storage of PBMCs and serum.

**15.2 Archival Tumor Biopsy for PD-1 and PD-L1 IHC**

Expression of PD-1 and PD-L1 in a pre-treatment tumor biopsy will be assessed using immunohistochemistry for PD-1 and PD-L1, to be performed internally at the Fred Hutchinson Cancer Center. This will be evaluated for correlation with outcomes.

**15.2.1 Collection of specimen(s)**

Samples of pre-treatment tumor biopsies will be requested from pathology internally, if available.

**15.2.2 Handling of specimen(s)**

Samples will be collected at room temperature and sent to the Experimental Histopathology resource at the Fred Hutchinson Cancer Center.

**16.0 STATISTICAL CONSIDERATIONS****16.1 Study Design**

The primary objective of the study is to determine the efficacy of nivolumab as measured by the overall response rate (ORR), in subjects with hematologic malignancies with relapsed or refractory disease after receipt of CAR T-cell therapy. ORR will be estimated, and its corresponding 95% exact binomial CI will be provided. The analyses of time-to event endpoints (DOR, PFS, and OS) will follow standard methodology by employing Kaplan-Meier and Cox proportional hazard model methodology.

Safety data will be summarized descriptively. Adverse events will be summarized by severity, seriousness, and relationship to study drug. Laboratory data will be compared to baseline values.

Additional exploratory data analyses will be conducted as appropriate.

The primary objective will be investigated by assessing if the true ORR is at least above some desirable target level following therapy with nivolumab. A subject is classified as response evaluable if they have at least one response assessment or if they discontinue from treatment due to death from any cause prior to obtaining at least one response assessment.

Based on the observations in Ansell 2018, the ORRs were low, e.g., 10% and 3% in the auto-HCT-failed and auto-HCT-ineligible, respectively. The desire is therefore to rule out a 5% ORR which will require around 25% ORR. If the sample size is 20, the study will have 85% power to detect the difference between the Null hypothesis of 5% ORR and the Alternative of 25% ORR, with a 1-sided alpha of 0.05.

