## 16.3 Statistical Consideration

Descriptive statistics, such as mean, standard deviation, and range for continuous variables, and percent and number for categorical variables, will be summarized for baseline information and demographic information. The statistical test for primary efficacy endpoint ORR will be performed using an exact binomial test for single proportion at the 5% one-sided significance level if appropriated.

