## 16.4 Stopping rules for toxicity and futility

In the event of a death on study that is deemed to be possibly, probably, or definitely attributable to the drug, further infusions will be suspended pending review by the DMC and consultation with the FDA. To further protect the safety of subjects, the study incorporates a stopping rule if the lower bound of a 1-sided 80% exact binomial confidence interval of the discontinuation rate due to medically significant Grade 3 or greater events that are possibly, probably, or definitely attributable to the drug is > 20%. Operationally, any of the following would trigger such a rule: 2 out of the first  $\leq 6$  subjects or 3 out of the first  $\leq 9$  subjects or 4 out of the first  $\leq 13$  or 5 out of the first  $\leq 16$  or 6 out of the first  $\leq 20$  subjects have unacceptable toxicity or  $\geq$  Grade 3 AEs that are possible, probably, or definitely attributable to

drug. If the true probability of  $\geq$  Grade 3 AE is 2.5%, the probability of study suspension under the above rule is approximately 0.01; if the true probability is 40%, the probability of suspension is approximately 0.91 (probabilities estimated from 5,000 simulations).

If this rule is met, further treatment for all subjects enrolled will be immediately halted. A safety evaluation will be performed and reviewed with the FDA and DMC prior to resuming any drug.

We are using a Simon's two-stage design (Simon, 1989) to stop early for futility. Based on the null hypothesis of 6% ORR and alternative hypothesis of 26% ORR, with a 1-sided alpha of 0.05, in the first stage, 12 subjects will be accrued. If there are 0 responses in these 12 subjects, then study will be stopped for futility. Otherwise, 8 or more additional subjects will be accrued for a total of 20 subjects. The null hypothesis will be rejected if 4 or more responses are observed in 20 subjects. This design (minimax) yields a type I error rate of 0.05 (one-sided) and power of 80%.

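### ORR is to be reported with a one-stage exact interval although the trial is two-stage; the upper limit is too low at 1/20, and the effect is minor elsewhere

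*Combined protocol and SAP*

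**What the plan says.** Section 16.1 gives the reporting plan for the primary endpoint: "ORR will be estimated, and its corresponding 95% exact binomial CI will be provided". Section 16.3 adds a test "using an exact binomial test for single proportion at the 5% one-sided significance level".

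Section 16.4 sets the sampling plan: "We are using a Simon's two-stage design (Simon, 1989) to stop early for futility". It is "Based on the null hypothesis of 6% ORR and alternative hypothesis of 26% ORR, with a 1-sided alpha of 0.05". The first stage has 12 subjects, and "If there are 0 responses in these 12 subjects, then study will be stopped for futility". The text goes on: "Otherwise, 8 or more additional subjects will be accrued for a total of 20 subjects". The final rule is: "The null hypothesis will be rejected if 4 or more responses are observed in 20 subjects".

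Section 16.1 states its own alternative of 25% ORR, against 26% in 16.4. It also defines a response-evaluable set. Neither the protocol text nor section 16 names an estimator, interval or p-value that takes the stage 1 stop into account.

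**The concern.** The ordinary exact (Clopper-Pearson) interval is exact for a fixed sample size. Here the sample size is 12 or 20, depending on the data. A total of 1/20 can arise only if the single response falls among the first 12 subjects; had it fallen among the last 8, the trial would have stopped at 0/12. The one-stage calculation counts those impossible paths and leaves out the early stop as a less favourable outcome. The interval then does not have the property its name claims, and at very low counts its upper limit is too low.

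At stake is what the report says about how much activity has been ruled out if nivolumab does little. At 1/20 the choice of interval decides whether the alternatives of 25% and 26% lie inside or outside it. That choice is better fixed before the data are seen.

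**Working it through.** **Inputs.** From 16.4: stage 1 n = 12, stop at 0, total 20, reject at 4 or more, null 6%, alternative 26%. From 16.1: alternative 25%, 95% exact binomial CI. Assumption: stage 2 has exactly 8 subjects.

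**1. The plan's own figures.** The probability of rejection is the sum over x = 1 to 12 of P(X1 = x; 12, p) × P(X2 ≥ 4 − x; 8, p). At p = 0.26 this is 0.8003, which reproduces the stated 80% power. At p = 0.06 it is 0.0286, within the stated 0.05.

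**2. Distribution of the outcome.**
- P(stop at 0/12) = (1 − p)^12.
- P(t/20) = p^t (1 − p)^(20 − t) × Σ C(12, x) C(8, t − x), summed over x ≥ 1.
- For t = 1 this is 12p(1 − p)^19. The one-stage model has 20p(1 − p)^19.

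The chance of ending at 1/20 is 12 × 0.06 × 0.94^19 = 0.22 at a true ORR of 6%. It is 0.16 at 10%, 0.013 at 25% and 0.010 at 26%.

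**3. Intervals.** The two-stage limits solve P(outcome this high or higher) = 0.025 and P(outcome this low or lower) = 0.025. The early stop is ordered lowest, then totals 1 to 20.

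| Result | Planned 95% CI | Two-stage exact 95% CI |
|---|---|---|
| 0/12 | 0 to 26.5% | 0 to 26.5% |
| 1/20 | 0.13% to 24.9% | 0.21% to 28.2% |
| 2/20 | 1.2% to 31.7% | 1.3% to 32.6% |
| 3/20 | 3.2% to 37.9% | 3.3% to 38.1% |
| 4/20 | 5.7% to 43.7% | 5.8% to 43.7% |

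From 5/20 up the two agree to 0.1 point.

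**4. Check at 1/20.** The probability of a result this low or lower:
- True ORR 25%, two-stage: 0.75^12 + 12 × 0.25 × 0.75^19 = 0.0317 + 0.0127 = 0.044.
- True ORR 25%, one-stage: 0.75^20 + 20 × 0.25 × 0.75^19 = 0.0032 + 0.0211 = 0.024.
- True ORR 26%: 0.0270 + 0.0102 = 0.037 two-stage, 0.019 one-stage.

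The two-stage values exceed 0.025 and the one-stage values do not. That is why only the planned interval leaves out 25% and 26%.

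**5. Error rates of the planned interval.** The true ORR was scanned from 0.5% to 60%.
- At 25% and 26% only 1/20 misses on the upper side, because the interval after 0/12 reaches 26.5%. The upper miss is 1.3% and 1.0%; two-sided coverage is 97.3% and 97.1%.
- Just above 26.46% both 0/12 and 1/20 miss. At 26.5% the upper miss is 0.735^12 + 12 × 0.265 × 0.735^19 = 0.0249 + 0.0092 = 0.034, the largest value found.
- Two-sided coverage is lowest at 27.15%: 1 − 0.0303 − 0.0247 = 0.945. It is below 95% only from about 26.5% to 27.2%.
- The upper miss also exceeds 2.5% up to 28.2%, and in short ranges where the true ORR lies between the planned and two-stage upper limits for a higher count (for example 31.7% to 32.6%). Two-sided coverage stays at 95% or more there.
- The two-stage interval has minimum coverage of 95.3% and an upper miss of at most 2.5% on the same scan.

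**The case against.** The case against acting is substantial, and most of it stands.

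- **Exclusion of the target.** A reader might infer that the planned interval rejects a drug that truly meets the target more often than it should. The documents' figures do not support that. If the true ORR is 25% or 26%, the upper limit falls below it 1.3% or 1.0% of the time, under the 2.5% allowed. At 1/20 the planned limit is 24.87%, only 0.13 point below 25%.
- **The point estimate.** A reader might infer that the simple proportion is also wrong and must be replaced by the uniformly minimum variance unbiased estimator (UMVUE). That is a preference. Averaged over all trials, including those stopped at 0/12, the simple proportion is low by 1.1 points at true ORRs of 5%, 6% and 10%. But its root mean squared error is smaller at an ORR of 5% (5.2 against 5.8 points) and at 6% (5.8 against 6.3). Among trials that reach 20 at a true ORR of 5%, the simple proportion averages 8.5% and the UMVUE 10.9%, so the UMVUE is further from the truth. At 1/20 the UMVUE is 1/12 = 8.3%, which gives the eight stage 2 non-responders no weight. Section 16.1 names no estimator.
- **Upper limits out of order.** The planned upper limit of 24.9% after 1/20 is below the 26.5% after 0/12. This is not in itself an error, since the two rest on 20 and 12 subjects.
- **Decisions.** The success rule is 4 or more in 20, and no section uses the upper limit. A one-stage test at that cut-off is slightly conservative here: 0.0290 one-stage against 0.0286 two-stage at 6%.

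What does not fall away is that the plan describes as exact an interval that does not hold its level under the plan's own design. At 1/20, a likely result if the drug is inactive, its upper limit is 3.3 points too low (28.2 − 24.9).

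**Conclusion.** The point holds for the interval, as a minor correction. Sections 16.1 and 16.4 do not match: one assumes a fixed sample, the other a two-stage sample. The practical effect is concentrated at 1/20. It is under 1 point in the upper limit at 2/20 (31.7% against 32.6%), 0.2 point at 3/20, and negligible from 4/20. After 0/12 the planned interval is already right. The coverage shortfall is at most 0.5 point, in a band of true ORR less than 1 point wide.

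The efficacy decision, the futility rule and the choice of point estimate are not in question. All figures assume 12 + 8 subjects with every subject counted in the denominator. Different attained stage sizes would shift them.

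**What to change.** In 16.1, replace the interval with wording such as: the 95% CI for ORR will be obtained by exact inversion of the two-stage distribution, with a stage 1 stop ordered below every result that reaches stage 2 and those results ordered by total responses; the attained stage sizes will be used. The last clause is needed because 16.4 leaves the stage 2 number open above 8 and 16.1 defines a response-evaluable set, so the final denominators may not be 12 and 20.

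Keep the simple proportion as the point estimate; the UMVUE may be shown as a supplement. Leave the rule of 4 or more in 20 as it is.

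The cost is one sentence and a few lines of code. The interval becomes slightly wider at 1 to 3 responses: 28.0 against 24.7 points at 1/20, and 31.3 against 30.5 at 2/20. No subjects or visits are added.

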## **9.0 STUDY INTERVENTIONS**

[figure not shown]
This is a single arm, unblinded phase II trial of nivolumab, a PD-1 inhibitor, for treatment of patients with hematologic malignancies (including B-cell non-Hodgkin lymphoma, chronic lymphocytic leukemia, and multiple myeloma) who either experience relapse or have persistent disease after treated with CAR T-cell therapy.

Approximately 20 subjects will be enrolled on this study, which will include a screening phase, an active treatment phase, and a follow-up phase. Before any study-related procedure can be performed, all

subjects must sign an informed consent form (ICF). Subjects will be evaluated for eligibility at screening.

The active treatment phase will extend from cycle 1, day 1, until study treatment discontinuation due to disease progression, initiation of subsequent anti-cancer therapy, unacceptable toxicity, withdrawal, or completion of study treatment. A study schema is depicted in figure 1.

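### Section 16.1 claims 85% power for 5% versus 25% ORR with 20 subjects; the planned exact test and decision rule give about 77%, and Section 16.4 gives the same rule 80% at the higher rate of 26%

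*Combined protocol and SAP*

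**What the plan says.** Section 16.1 sets the target for the primary endpoint: "The desire is therefore to rule out a 5% ORR which will require around 25% ORR". It then justifies the sample size: "If the sample size is 20, the study will have 85% power to detect the difference between the Null hypothesis of 5% ORR" and an alternative of 25%, at a one-sided alpha of 0.05. It does not say how the 85% was calculated.

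Section 16.3 names the test of ORR, which "will be performed using an exact binomial test for single proportion at the 5% one-sided significance level if appropriated".

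Section 16.4 describes a Simon two-stage design for the same endpoint and the same 20 subjects, with other hypotheses: "Based on the null hypothesis of 6% ORR and alternative hypothesis of 26% ORR, with a 1-sided alpha of 0.05". The trial stops if there are no responses in the first 12 subjects. At the end, "The null hypothesis will be rejected if 4 or more responses are observed in 20 subjects". The stated properties are: "This design (minimax) yields a type I error rate of 0.05 (one-sided) and power of 80" per cent.

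On the final number, Section 16.4 says "Otherwise, 8 or more additional subjects will be accrued for a total of 20 subjects", and Section 9.0 says "Approximately 20 subjects will be enrolled on this study".

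**The concern.** One endpoint, one sample size and one rejection cut-off carry two hypothesis pairs and two powers, and nothing in the plan links them. The two statements cannot both be true. For a fixed rule that rejects on a high response count, power rises with the true response rate. A rule with 80% power at 26% must have less than 80% at 25%, so it cannot have 85% there.

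At stake is how well the study is said to be protected against missing a useful drug. Anyone who judges the sample size from Section 16.1, or later interprets a negative result, would take the risk of missing a 25% ORR to be 15%.

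**Working it through.** **Inputs.** n = 20, null 5%, alternative 25%, one-sided alpha 0.05, stated power 85% (Section 16.1). Exact binomial test (Section 16.3). Null 6%, alternative 26%, stop at 0/12, reject at 4 or more of 20, stated alpha 0.05 and power 80% (Section 16.4).

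**1. Can the 85% be reproduced?** Not with the planned test. Some methods that the plan does not name come near it at 5% versus 25%, n = 20, one-sided 0.05:

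- Arcsine: h = 2·asin(√0.25) − 2·asin(√0.05) = 0.596. Power = Φ(0.596·√20 − 1.645) = Φ(1.021) = 84.6%.
- Normal approximation with continuity correction: 83.6%.
- Normal approximation without correction: 89.2% at one-sided 0.05, 86.0% at two-sided 0.05.

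The figure probably comes from an approximation. The expected number of responses under the null is only 20 × 0.05 = 1, so a large-sample formula is a poor guide to the exact test.

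**2. Cut-off of the exact test under the 5% null, n = 20.**

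| Reject if responses are at least | Alpha at 5% | Power at 25% |
|---|---|---|
| 3 | 0.0755 (above 0.05) | 90.9% |
| 4 | 0.0159 | 77.5% |
| 5 | 0.0026 | 58.5% |

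The cut-off must be 4, as in Section 16.4. No cut-off gives 85%.

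Power at 25%: P(X ≥ 4) = 1 − (0.0032 + 0.0211 + 0.0669 + 0.1339) = 1 − 0.2251 = 0.775.

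**3. Add the futility stop.** The stop removes those outcomes with 0 of the first 12 and at least 4 of the next 8. Two-stage rejection probability = P(X ≥ 4 of 20) − (1 − p)^12 × P(Y ≥ 4 of 8).

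At 25%: 0.7748 − 0.0317 × 0.1138 = 0.7748 − 0.0036 = 0.7712.

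| True ORR | Single stage, ≥4/20 | Two-stage, 0/12 then ≥4/20 |
|---|---|---|
| 5% | 0.0159 | 0.0157 |
| 6% | 0.0290 | 0.0286 |
| 25% | 0.7748 | 0.7712 |
| 26% | 0.8038 | 0.8003 |

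The stop costs about 0.4 points. The rest of the gap to 85% comes from the discreteness of the exact test. The two-stage rule reaches 85% power only at a true ORR of about 28.0%.

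**4. Check Section 16.4.** At 6% versus 26% the rule has exact power 80.0% and attained alpha 0.029, so the stated 0.05 is a ceiling. A search for the smallest total N with alpha ≤ 0.05 and power ≥ 80% returns N = 20, 0/12, ≥4/20 for this pair. The minimax label is right. For 5% versus 25% the same search returns N = 16 (0/12, ≥3/16; alpha 0.043, power 80.1%), so the label would not carry over to that pair.

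**5. Could another exact design of this size give 85%?** Over exact non-randomised single-stage designs and two-stage designs that stop early only for futility, with N from 10 to 20 and alpha ≤ 0.05, the highest power at 5% versus 25% is 83.3% (0/12, ≥3/17, alpha 0.0496). With the cut-off of 4 and the 0/12 stop, 85% needs 23 subjects (85.4%, alpha 0.025 at 5%).

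**6. The additional-subjects wording (minor).** With the cut-off held at 4 after the 0/12 stop, alpha at 6% is 0.0286 at N = 20, 0.0335 at 21, 0.0388 at 22, 0.0445 at 23 and 0.0505 at 24.

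**The case against.** The best defence is that Section 16.4 is the operative design and is correct as written. A reader of that section sees 80%, and the 85% is an approximate planning figure in a small trial that Section 5.1 calls a pilot. Section 16.3 also qualifies its exact test. The practical consequence is indeed small, since no decision rule depends on the 85%. But Section 16.1 states the figure without qualification as the power of this study and names no approximation, and the plan does not say that 6% versus 26% replaces 5% versus 25%. The qualification in Section 16.3 does not help either, because the fixed rule in Section 16.4 gives 77.1% at 25%.

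A second objection is that only the 5% null has a stated reason: Section 16.1 derives it from ORRs of 10% and 3% in an earlier nivolumab study, while Section 16.4 gives no reason for 6% or 26%. This stands. The choice of pair is the sponsor's, and moving to 6% versus 26% should come with a reason for those rates.

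Third, the source of the 85% cannot be established, because several methods come near it. This also stands, but the conclusion does not depend on the source.

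Fourth, the wording on additional subjects is a separate ambiguity. The same sentence fixes the total at 20, and alpha at 6% stays below 0.05 up to 23 subjects. It adds no weight to the main point.

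**Conclusion.** The concern holds. Power at 25% ORR is 77.5% by the exact test and 77.1% by the two-stage rule, 7.5 to 7.9 points below the stated 85%. The chance of missing a true 25% ORR under the rule is 22.9%, about half as large again as the implied 15%. The figure in error is the one in Section 16.1; the power and minimax label in Section 16.4 reproduce.

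The consequence is limited. Four or more responses in 20 rejects a 5% null at attained alpha 0.016 and a 6% null at 0.029, so a positive result is valid under either pair. The calculation assumes independent subjects with a common response rate, exactly 20 subjects in the final count, and the cut-offs of Section 16.4 applied as written. It should be fixed, and confidence is high.

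**What to change.** Use one hypothesis pair in Sections 16.1 and 16.4, and state its exact power and attained alpha.

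- **Simplest:** in Section 16.1, replace 5% versus 25% and 85% with the Section 16.4 values: 6% versus 26%, power 80.0%, attained one-sided alpha 0.029. Add a sentence on why 6% and 26% were chosen.
- **If 5% versus 25% is kept:** state power of 77% and attained alpha of 0.016, re-base Section 16.4 on that pair, and drop its 80% and its minimax label.

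Also clarify whether more than 8 subjects may be added in the second stage, for example to allow for subjects who are not response evaluable, and state the number to which the cut-off of 4 applies.

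The cost is wording in the statistical section and a less favourable stated power. The sample size of 20, the futility stop and the rejection rule do not change.

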## 16.2 Objectives

### Primary Objectives

- To assess the efficacy of nivolumab, a PD-1 inhibitor, in subjects with hematologic malignancies with relapsed, refractory, or detectable disease after receipt of CAR T-cell therapy
- To assess the safety of administering nivolumab, a PD-1 inhibitor, in subjects with hematologic malignancies with relapsed or refractory disease after receipt of CAR T-cell therapy

### Secondary Objectives

- To determine overall survival, progression free survival, and duration of response after treatment with nivolumab

### Exploratory Objectives

- To determine cytokine response after treatment with nivolumab
- To determine PD1 and PD-L1 expression patterns in pre-treatment tumor biopsy and correlate with response
- To collect peripheral blood samples for future biomarker analyses

